Adolescents who participate in all 3 weekly exercise sessions will have the potential to accumulate ~90 min. of MVPA/wk. (~13 min./d). Thus, MVPA outside these sessions will be required to meet weekly recommendations. Health coaches will provide weekly challenges in the form of meeting a goal for increased steps, trying a new activity, or creating and performing their own exercise routine etc. Scheduled group sessions will be reduced to 1/wk. during mos. 7-12, thus the volume of MVPA to be completed outside the group session, i.e., "homework" will increase to meet the recommended daily MVPA. Participants will be provided Dropbox access to previous exercise sessions they can complete on their own to meet weekly MVPA goals, if desired. Information regarding increasing PA, available from the National Center on Health, Physical Activity and Disability (NCHPAD) and the Special Olympic athletes home training guide, and similar material appropriate for parents, will also be loaded on the iPads of both intervention arms.

Parental Involvement

AO Arm. One parent/guardian will be asked to attend the orientation session, monitor MVPA across the intervention, and complete survey instruments at baseline, 6, 12, and 18 mos. (See assessments). By design, parental involvement in the AO group will be limited to reminder contacts (phone/text/email) from the health coach if their adolescent misses 2 consecutive exercise sessions. Contact attempts will be limited to 3 for each occurrence.

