Exploratory aims. If there are no between arm differences in the longitudinal change in MVPA across 18 mos., general mixed models will be fitted for the two arms combined to examine the association for the process variables/participant characteristics with MVPA. These variables include: attendance at group video (AO-adolescent; A+P-adolescent/parent) and education/support sessions (A+P only), self-monitoring of PA (AO-adolescent; A+P-adolescent/parent), parental use of Facebook page (A+P only), peer interactions/support during group PA sessions, adolescent self-efficacy, social support and barriers for PA, parental MVPA, beliefs and attitudes toward PA and parental time constraints, age, sex, and IDD diagnosis. However, if there is a significant group difference in MVPA, we will determine whether the previously listed process variables/participant characteristics explain/attenuate the intervention effect, i.e., moderation, by testing a 2-way interaction with the group effect and/or a 3-way interaction with the group-by-time interaction term. Some covariates will be measured only at baseline (age, sex, IDD diagnosis), some will be summarized across the trial (attendance at group video and education/support sessions, self-monitoring of PA, parental use of Facebook page, peer interactions/support during group PA sessions), while others will be assessed at specific time points (BMI, adolescent self-efficacy, social support and barriers for PA, parental MVPA, beliefs and attitudes toward PA and parental time constraints). Thus, we will carefully design our models to assure the appropriateness of the analysis. All analyses will be conducted using R and SAS 9.4 or higher.

Missing data. Missing due to either attrition, e.g., participant dropout or nonresponse, will be handled by multiple imputation, in which an expectation-maximization (EM) algorithm supplies prior estimates of missing values for a subsequent Monte Carlo Markov Chain (MCMC) procedure ⁶⁰. A sufficient number of imputed datasets will be created to ensure accurate recovery of missing data; and analysis results from each imputed dataset will be combined to make valid statistical inferences. All measured variables will be incorporated into the imputation process as auxiliary variables, thereby satisfying the missing at random (MAR) assumption ⁶¹.

REFERENCES

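### The exploratory plan tests group interactions that cannot be estimated for A+P-only variables, uses interactions where the question is mediation, and picks its model by an 18-month test that was not powered

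*Combined protocol and SAP*

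**What the plan says.** All of this is in the Exploratory aims paragraph of the section Analysis plan and statistical power, which sets out two branches.

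- **No arm difference.** "If there are no between arm differences in the longitudinal change in MVPA across 18 mos", then "general mixed models will be fitted for the two arms combined" to relate the process variables and characteristics to MVPA.
- **Significant arm difference.** The plan asks whether the same listed variables account for or weaken the intervention effect. It calls this moderation and proposes "testing a 2-way interaction with the group effect and/or a 3-way interaction with the group-by-time interaction term".

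The list marks some variables as belonging to one arm: "education/support sessions (A+P only" and "parental use of Facebook page (A+P only". Others have a parent part in A+P only, for example "attendance at group video (AO-adolescent; A+P-adolescent/parent"; self-monitoring is listed the same way. No variable is exempted from the interaction tests.

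The design explains the labels. Table 1 enters NA for AO under parent contacts and the parent Facebook group. The AO Arm text under Parental Involvement says: "By design, parental involvement in the AO group will be limited to reminder contacts (phone/text/email) from the health coach".

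The paragraph also says that attendance, self-monitoring, Facebook use and peer interaction are summarised over the trial, while age, sex and IDD diagnosis are baseline only. Its sole safeguard is a general promise to design the models with care.

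**The concern.** There are three linked problems.

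1. A variable that exists in one arm cannot interact with arm. The instruction cannot be carried out for those variables.
2. Whether a variable arising after randomisation accounts for the effect is a mediation question. An interaction asks whether the effect differs across levels of a variable, which is read most safely when the variable is fixed before randomisation.
3. A non-significant result from a comparison without planned power is weak ground for treating the arms as one population. If group is then left out, a process variable that differs by arm can stand in for arm.

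The exploratory aims are meant to identify what drives change in MVPA. At stake is whether a reported factor is a real association or only arm membership.

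**Working it through.** **Estimability.** Let g be group (AO = 0, A+P = 1), x an A+P-only variable and t time.

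- Two-way model, columns {1, g, x, gx}. If AO is coded 0, then gx = x in every row, so rank is 3 of 4. If AO is missing and dropped, g = 1 throughout, so g repeats the intercept and gx repeats x; rank is 2 of 4.
- Three-way model, columns {1, t, g, x, tg, tx, gx, tgx}. With AO coded 0, gx = x and tgx = tx, so rank is 6 of 8. With AO dropped, four pairs coincide and rank is 4 of 8.

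A numerical check of the design matrices with 57 per arm gave the same ranks. Only the slope of x within A+P can be estimated. No AO family (0 of 57) informs the interaction. Variables observed in both arms do not have this problem.

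**Which variables suit a moderation test.** Age, sex and IDD diagnosis are fixed at baseline. Parental MVPA is measured at month 0 and every 3 months after (Outcome Assessments, MVPA), so its baseline value qualifies and later values do not. Attendance, self-monitoring, Facebook use and peer interaction arise only after randomisation.

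**The plan's own power figure.** Inputs from the Power paragraph: difference 10 min/d, SD 35 min/d, N = 114, m = 21 measurements, r = 0.25. Alpha is not stated; 0.05 is assumed.

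- f = 10/(2 × 35) = 0.1429, given as 0.14.
- Noncentrality for the overall group effect: λ = f²·N·m / [1 + (m − 1)r] = 0.02041 × 114 × 21 / (1 + 20 × 0.25) = 8.14.
- F test on 1 and 112 df: power 80.8%. The stated 81% is reproduced.

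**Power of the 18-month test that selects the branch.** The plan gives no figure. Two readings can be tied to 10 min/d.

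*Reading A: overall group effect, the plan's method, effect sustained.* The Secondary Aim analysis uses 7 days at 7 time points, so m = 49.

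- λ = 0.02041 × 114 × 49 / (1 + 48 × 0.25) = 8.77; power 83.5%.
- Arms combined despite a true 10 min/d: 100 − 83.5 = 16.5%, about 16%.
- At 7.5 min/d power is 59.6%, and at 5 min/d 31.2%. Group sessions stop after month 12, so some fading is possible.

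*Reading B: difference in change, as the trigger is worded.* Take 35 min/d, described as the SD of change, and assume that it holds at 18 months.

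- Standard error = 35 × √(2/57) = 6.56; 10/6.56 = 1.53; two-sided power about 33%.
- Arms combined despite a true 10 min/d: about 67%. Reaching 80% power on this reading would need 193 per arm.

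**If group is left out of the combined model.** Simulation, 4,000 trials per setting: true arm difference 10 min/d, SD 35, an A+P-only variable scaled 0 to 1 (mean 0.5 or 0.7, SD 0.2) coded 0 in AO, with no effect within A+P. Among trials sent to the combined branch, the average slope was 9.9 or 8.1 min/d instead of 0. It was significant in 6.9% or 5.6% of them, so the main harm is a misleading estimate, not frequent false significance.

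**The case against.** The strongest reply is that this is exploratory, that the plan itself flags the A+P-only variables and promises suitable models, and that a rank-deficient term shows up at fitting and does not silently bias a result. That stands as a limit on severity. It does not say what the analyst should do instead.

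Several stronger readings are tempting, and the documents do not support them.

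- *Two trials in three would wrongly combine the arms.* That is Reading B alone. The plan's own method gives about 16% for a sustained effect. The two figures are not outer limits either. The plan's interaction calculation at f = 0.09 gives 89% with 21 measurements and would give 99.6% with 49, but that f is not linked to any difference in min/d.
- *Imputation would create AO values for A+P-only variables.* The sentence "All measured variables will be incorporated into the imputation process as auxiliary variables" may suggest it. However, the Missing data paragraph addresses attrition and nonresponse, and Baseline equivalence speaks of missing outcome data. A component absent by design is neither.
- *Parental MVPA is purely post-randomisation.* It has a baseline value.
- *The combined model drops group.* The text is silent. The Secondary Aim analysis does state that its time-varying covariate model controls for group, so the contrast supports asking for clarity and no more.
- *The plan mislabels its test.* An interaction is a moderation test. The mismatch is with the stated question, and only for post-randomisation variables.

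One sentence in Overview of study design gives adolescents in both arms weekly education/support sessions in months 7-12. It conflicts with Table 1 and with the A+P-only label, and the passages must be reconciled. The point here rests on the label in the analysis section.

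**Conclusion.** The concern holds in this form. The stated interaction rule cannot be carried out for education/support attendance, Facebook use and the parent parts of attendance and self-monitoring; this is algebra and needs no assumption beyond the A+P-only labels. For post-randomisation variables, the interaction does not answer the stated question.

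The choice of branch rests on an 18-month comparison for which the Power paragraph disclaims power, as it does for all secondary aims. At a true 10 min/d the arms would be combined about 16% of the time (49 measurements, r = 0.25, effect sustained) or about 67% (change score, SD 35 carried to 18 months), with alpha 0.05 assumed in both. That the first branch means non-significance is inferred from its pairing with a significant difference. The two triggers also differ in wording, one naming longitudinal change and the other a group difference in MVPA.

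The consequences are confined to the exploratory aims. The primary 6-month analysis is unaffected. The plan should be changed because it is wrong as written and the remedy is small.

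**What to change.** Amend the Exploratory aims paragraph as follows.

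1. Analyse education/support attendance, Facebook use and the parent parts of attendance and self-monitoring within A+P only, as associations.
2. Limit group and group-by-time interaction tests to baseline characteristics and baseline values of repeated measures, including baseline parental MVPA.
3. For post-randomisation variables present in both arms, specify a mediation analysis, or report associations adjusted for group without claiming that they explain the effect.
4. Keep group and group-by-time in every exploratory model fitted to both arms, whatever the 18-month p-value. The two-branch rule can then be removed.

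The cost is a wording change, fewer interaction tests and slightly more analysis work. No new data are needed.

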Power. This trial is powered to detect a between arm difference (AO vs. A+P) in the change of MVPA (0-6 mos.) of 10 min./d. This represents an additional 70 min. of MVPA/wk. An increase in MVPA of this magnitude is associated with improved adiposity and cardiovascular fitness in typically developing adolescents^{56, 57}, and potentially in adolescents with IDD, a group with low baseline levels of MVPA^{58, 59}. Statistical power to detect a significant effect on MVPA across 6 mos., the primary aim in the proposed 2-arm randomized design, depends on the following parameters: the number of participants in each arm (J), the number of measurements ($n = 21$; 7 days at 0, 3, and 6 mos.), correlations among repeated measures (r), and effect size (f). Assuming a conservatively large standard deviation for change in MVPA in both arms (35 min./d), corresponds to a small to moderate effect size ($f = 0.14$). The correlation between repeated measures of MVPA (3 mo. interval) in our pilot trial was $r = 0.22$. To be conservative, we assumed a higher correlation ($r = 0.25$) for this sample size calculation. Based on these assumptions, power analysis using G*Power 3.1.9.2 shows a sample of 114 adolescents ($J = 57/\text{arm}$) would provide 81% power to test overall between arm differences across time, i.e., group effect. This sample size would also provide $\geq 80\%$ power to detect a group difference in change, i.e., time-by-group interaction, as small as $f = 0.09$. Missing data will be fully recovered via multiple imputation as discussed subsequently, which will remove or minimize (if present) confounding effects of missingness on our statistical power. The secondary aims were not powered to detect between group differences.

Baseline equivalence. We will compare baseline characteristics, e.g., age, sex, race/ethnicity, BMI, IDD diagnosis, etc., between the AO and A+P arms using independent-samples *t*-test for continuous variables and chi-square/Fisher test for categorical variables, to assess the degree to which randomization resulted in equivalent groups. Variables that demonstrate a significant nonequivalence will be controlled for in our analytic models to improve the accuracy in estimates of the intervention effect. Prior to modeling, missing data for each outcome will be imputed as described subsequently.

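### The planned imputation makes no provision for group-by-factor terms; in its ordinary form it would pull the exploratory moderation tests toward zero

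*Combined protocol and SAP*

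**What the plan says.** All the text is in the combined protocol and SAP, section Analysis plan and statistical power.

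- **Order of steps** (Baseline equivalence): "Prior to modeling, missing data for each outcome will be imputed as described subsequently".
- **Scope** (Missing data): "Missing due to either attrition, e.g., participant dropout or nonresponse, will be handled by multiple imputation".
- **Method** (Missing data): "an expectation-maximization (EM) algorithm supplies prior estimates of missing values for a subsequent Monte Carlo Markov Chain (MCMC) procedure".
- **Variables entered** (Missing data): "All measured variables will be incorporated into the imputation process as auxiliary variables, thereby satisfying the missing at random (MAR) assumption".
- **Expected result** (Power): "Missing data will be fully recovered via multiple imputation as discussed subsequently". No expected missing share is given.
- **Moderation tests** (Exploratory aims): "if there is a significant group difference in MVPA, we will determine whether the previously listed process variables/participant characteristics explain/attenuate the intervention effect", and this is done "by testing a 2-way interaction with the group effect and/or a 3-way interaction with the group-by-time interaction term".

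No sentence says that products of group with a factor, or of group, factor and time, enter the imputation. None says that imputation is done separately by arm. Neither is ruled out.

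**The concern.** EM followed by MCMC is ordinarily a single multivariate-normal model, linear in the variables supplied. A list of all measured variables does not normally include derived products. Under that model, age, sex, diagnosis, self-efficacy and the other factors each have one slope on MVPA, shared by the two arms. Values imputed this way carry little or none of the arm-specific slope that the exploratory analysis then looks for. More imputed datasets do not help, and neither do more auxiliaries that carry no interaction themselves.

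Finding the factors that influence change in MVPA over 18 months is a named aim. Several features make loss of whole waves plausible: the plan itself names dropout and nonresponse, monitors are mailed at 3, 9 and 15 months, and the last six months have no contact. If the estimates are pulled toward zero, a null moderation result is hard to interpret.

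**Working it through.** **The plan's own figure.** The plan is "powered to detect a between arm difference (AO vs. A+P) in the change of MVPA (0-6 mos.) of 10 min./d", with SD 35, 21 measurements, r = 0.25 and N = 114. Alpha is not stated; 0.05 is assumed. f = (10/35)/2 = 0.1429. Noncentrality = N f² m / (1 + (m − 1) r) = 114 × 0.0204 × 21 / 6 = 8.14 on 1 and 112 df, which gives 80.8% power (79.2% with f rounded to 0.14). The stated 81% is reproduced. It concerns the group effect and says nothing about moderation.

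**Assumptions for what follows.** The missing share p is 10%, 20% or 30%. Missingness is completely at random. The factor is fully observed. Imputation is joint-normal with no product terms.

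**Step 1: no other wave carries the interaction.** Let δ be the true difference in slope between arms. Observed cases show δ and imputed cases show 0, so the estimate is (1 − p)δ + p × 0. The share kept is 1 − p: 0.90, 0.80, 0.70. A large-sample simulation (n = 200,000, one outcome) gave 0.90, 0.82, 0.67. Dropout after baseline behaves the same way, because baseline MVPA contains no intervention interaction.

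**Step 2: an intermediate wave is observed.** Suppose waves 0, 3 and 6 have equal correlation ρ and only month 6 is missing. The imputation regresses month 6 on each earlier wave with coefficient c = ρ/(1 + ρ). If month 3 shows a fraction h of the month-6 interaction, the imputed cases carry c × h of it, and the share kept is 1 − p(1 − c h). With h = 0.5:

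- ρ = 0.25: c = 0.20, c h = 0.10; kept 0.91, 0.82, 0.73.
- ρ = 0.80: c = 0.444, c h = 0.222; kept 0.92, 0.84, 0.77.

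**Step 3: three-wave simulation** (n = 200,000, ρ from 0.25 to 0.80, h = 0.5, simulation error about 2 points). Share of the interaction kept:

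| Missing | Dropout after baseline, no products | Month 6 only, no products | Group-by-factor product included |
|---|---|---|---|
| 10% | 0.90-0.92 | 0.91-0.94 | 1.00-1.01 |
| 20% | 0.78-0.80 | 0.81-0.85 | 0.99-1.01 |
| 30% | 0.70-0.71 | 0.71-0.78 | 0.96-1.02 |

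A further three-wave run covering dropout and intermittent whole-wave loss kept 0.90-0.95, 0.79-0.87 and 0.68-0.84, against 0.97-1.05 with imputation by arm. Subtracting from 1 gives losses of 5-10%, 13-21% and 16-32%. The two sets agree within simulation error.

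**Step 4: scattered missing days.** With some days missing inside waves that are otherwise observed, 0.90-0.98 was kept at 10% missing and 0.83-0.94 at 20%.

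**Step 5: what it does to power (illustration).** One outcome per adolescent, 57 per arm, true interaction 0.50 SD per SD of the factor, 20 imputations, 500 runs, and two settings of the auxiliary variable:

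| Missing | Pooled, no products | By arm | Observed data only |
|---|---|---|---|
| 10% | 58-68% | 68-72% | 68-72% |
| 20% | 43-48% | 60-63% | 60-62% |
| 30% | 30-34% | 56-59% | 56-58% |

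The 0.50 is assumed. It is large next to the trial's planned main difference of 10/35 = 0.29 SD. The one-outcome design also omits the help from other waves, so this table shows the upper end of the damage.

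**The case against.** **Additivity is not stated.** A reader might infer that the plan specifies an additive imputation. It does not; it is silent, and an analyst could add products or impute by arm without departing from the text. This stands, and the point is conditional on it. The promise in Exploratory aims to design the models carefully does not fill the gap, because it follows a list of when each covariate is measured and concerns the analysis models.

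**The loss need not be proportional.** A reader might take the loss to equal the missing share throughout. That is close to the upper limit. Each adolescent has up to 21 daily values by month 6. If r = 0.25 held between all 21 days, 7-day means would correlate 7 × 0.25 / (1 + 6 × 0.25) = 0.70 between waves. With months 3 and 6 missing independently and equal moderation at both, 0.95, 0.87 and 0.82 was then kept at 10%, 20% and 30% missing. This also stands, although shrinkage remains in every whole-wave setting and is near-proportional for dropout.

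**The consequence can be overdrawn.** It does not follow that the trial will report no moderators, only that real ones are more likely to be missed. At 10% missing the loss is small. The tests are exploratory and run only after a significant group difference.

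**The primary result.** A reader might extend the bias to the primary comparison. Where group and every wave of MVPA are in the imputation model, arm means by wave are free to differ, so this mechanism does not reach it.

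**A likelihood analysis is not a full answer.** Self-efficacy, barriers and parental MVPA can be missing along with the adolescent's MVPA, and fitting observed outcomes does not handle missing covariates. This is correct, and the fix allows for it.

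**Conclusion.** The concern holds in conditional form. Unless group-by-factor terms are included or imputation is by arm, the planned imputation biases the exploratory 2-way and 3-way moderation estimates toward zero. For whole-wave loss the bias is roughly 5-10%, 13-21% and 16-32% at 10%, 20% and 30% missing. It is near the missing share for dropout, and often smaller for scattered missing days. The claim of full recovery in the Power paragraph does not extend to these tests.

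The figures rest on assumed missing shares, data missing completely at random, fully observed factors and the ordinary joint-normal model. A different missingness mechanism would change the sizes. Severity is low, because the tests are exploratory and conditional, but a better method is available at little cost.

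**What to change.** Add to Missing data, with a cross-reference in Exploratory aims, for the interaction models only:

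- Impute separately within each arm, using a short variable list specific to the model that includes the repeated MVPA values.
- Where the factor is fully observed (age, sex, IDD diagnosis), the alternative is to fit the planned mixed model by likelihood to the observed MVPA. This needs no imputed outcomes under missing at random.
- For factors that can themselves be missing (self-efficacy, barriers, parental MVPA), use the by-arm imputation.
- Keep the planned imputation for the main-effect analyses.

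Facebook use and education/support sessions exist only in A+P. No interaction with group can be estimated for them, so they fall outside this change.

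The cost is some SAP wording and one extra imputation run, or none where the likelihood option is used. The downside is fewer auxiliaries, which weakens the all-variables argument for missing at random. Over 18 months, 7 waves × 7 days = 49 daily MVPA values, close to the 57 adolescents in an arm, so the list has to be kept short.
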